3.0 DRUG INFORMATION

There are no drugs associated with this study.

4.0 PATIENT SELECTION

4.1 Patient eligibility

- 4.1.1 Any patient undergoing autologous or allogeneic HSCT at The Blood and Marrow Transplant Program at Northside Hospital will be eligible.
- 4.1.2 Patients must have a single primary caregiver.
- 4.1.3 Patient must be willing to comply with all assessments as outlined in the protocol.
- 4.1.4 Patient must be willing to sign informed consent.

4.2 Caregiver eligibility

- 4.2.1 Must be the primary caregiver for an autologous or allogeneic HSCT patient at The Blood and Marrow Transplant Program at Northside Hospital.
- 4.2.2 Caregiver must be willing to comply with all assessments as outlined in the protocol.
- 4.2.3 Caregiver must be willing to sign consent.

5.0 TREATMENT PLAN

Pre-BMT Patient Completes: BSI-18, BFI, BPI
Caregiver Completes: Demographic Form, BSI-18, BFI, Burden Interview

Days 0, 7, 30 and 365 Patient Completes: BSI-18, BFI, BPI
Caregiver Completes: BSI-18, BFI, Burden Interview

	Pre-BMT	Day 0	Day 7 ³	Day 30 ³	Day 365 ⁴
Demographics ¹	X				
BSI-18	X	X	X	X	X
BFI	X	X	X	X	X
BPI ²	X	X	X	X	X
Burden Interview ¹	X	X	X	X	X

¹caregiver only

²patient only

³assessment to be done +/- 3 days

⁴assessment to be done +/- 7 days

6.0 ADVERSE EVENT REPORTING

Adverse events are further defined as “Any untoward medical occurrence in a patient or clinical investigation subject administered a pharmaceutical product and which does not necessarily have to have a causal relationship with this treatment.”¹⁵

Patients will be monitored by the investigators and data maintained by the Clinical Research Program. All Adverse Events will be graded with the Common Terminology Criteria for Adverse Events (CTCAE) Version 3.0.

http://ctep.cancer.gov/protocolDevelopment/electronic_applications/docs/ctcae3.pdf

Due to the non-treatment nature of this protocol, there are not expected to be any adverse events. However, should a patient experience an adverse event that is specifically related to participation in this study, the following reporting criteria will apply. Patients will be followed through Day 365 for protocol-related adverse events.

6.1 Procedure for reporting Serious and Unexpected Adverse Events

Serious Adverse Events will be reported by telephone or email to the Institutional Review Board within 24 hours of notification of event. Written report will follow within 10 working days. Serious adverse events will be reported for a period of one (1) year post-transplant.

6.2 Definition of Serious and Unexpected Adverse Events:

Serious Adverse Events are defined as one of the following:

- a. Death
- b. Life-Threatening
- c. Hospitalization (initial or prolonged)
- d. Disability
- e. Congenital Anomaly
- f. Requires Intervention to Prevent Permanent Impairment or Damage

Unexpected is defined as:

Not previously reported with the agents/devices or procedures being undertaken. Symptomatically and pathophysiologically related to known toxicity but differs because of greater severity than previously reported.

7.0 RISKS and TOXICITIES

7.1 There are no expected risks associated with participation in this study. However, there may be an indirect or direct increase in psychological distress related to the completion of the psychological measures. Patients and caregivers will be monitored per programmatic protocol for any increases in psychological distress and these symptoms will be managed according to programmatic standards. All participants will be asked to contact the principal investigator, who is a licensed psychologist, if they experience an increase in psychological distress.

8.0 STATISTICAL CONSIDERATIONS/DATA ANALYSIS

8.1 We will plan to accrue 50 autologous and 50 allogeneic patient/caregiver dyads. This number of patients will be sufficient to perform an initial analysis to examine levels of distress and associated outcome variables. We expect that patients will be accrued over 1-2 years.

8.2 Data analysis will be performed on the information gathered to evaluate the impact of HSCT on the caregiver's level of burden, depression, anxiety, somatic symptoms, fatigue and overall distress. It will also examine if caregiver burden leads to an increase in the patient's hospital utilization and overall outcome. In addition, we hope to identify these caregiver symptoms as they relate to the patient's overall functioning. The analysis will include t-tests to look at correlations, as well as more complex statistical procedures (e.g., manova, and multiple regression analyses) to identify relationships between variables.

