1.0 OBJECTIVES

Primary Objectives:

1.1 To investigate the level of distress and feelings of burden in caregivers of HSCT patients.

Secondary Objectives:

1.2 To investigate the impact of patient distress, fatigue and pain on the level of caregiver distress and burden.

1.3 To investigate the impact of caregiver distress and burden on overall patient survival and length of patient hospitalization.

1.4 To identify common characteristics of caregivers who report significantly more feelings of burden or distress.

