in the HSCT process. The current literature on HSCT caregivers suggests that caregivers for HSCT patients do report feeling stressed, exhausted emotionally and physically, and in need of support^{2,3,4}. One study identified high levels of stress and depression pre-transplant⁵. A 2004 study by Gaston-Johansson⁶ found that primary caregivers of patients with breast cancer scheduled for BMT experience fatigue, anxiety, burden of care, and low quality of life.

Due to these previous findings, it was clear that level of burden, fatigue and distress were essential properties to be measured in HSCT caregivers. Each of these areas will be measured by a specific, psychometrically sound instrument. The Burden Interview, The Brief Fatigue Inventory, The Brief Pain Inventory and the Brief Symptom Inventory-18^{7, 8, 9, 10, 11, 12, 13, 14} were selected due to their previous use in oncology settings.

The purpose of this study is to examine the impact of HSCT on the caregiver's level of burden, depression, anxiety, somatic symptoms, fatigue and overall distress. It will also examine if caregiver burden leads to an increase in the patient's hospital utilization and overall outcome. In addition, we hope to identify these caregiver symptoms as they relate to the patient's overall functioning. Therefore, each patient will also complete self-report measures in order to assess if the patient's level of distress impacts the caregivers' functioning. The patients will complete self-report measures assessing symptoms of psychological distress, pain and fatigue and these scores will be matched to their particular caregiver.

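### Objective 1.3 has no stated patient covariates and no listed clinical severity variable, so an unadjusted burden–outcome link may reflect how sick the patient is

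*Combined protocol and SAP*

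**What the plan says.** Objective 1.3 in section 1.0 is "To investigate the impact of caregiver distress and burden on overall patient survival and length of patient hospitalization". Section 8.2 turns this into a causal question: "It will also examine if caregiver burden leads to an increase in the" patient's use of hospital and the overall outcome. Section 2.0 uses the same causal wording.

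The data source in section 8.2 is given only in general terms: "Data analysis will be performed on the information gathered". The methods named are t-tests, MANOVA and multiple regression. No covariate is named, and none of the five burden assessments is singled out as the exposure.

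The section 5.0 schedule lists three patient questionnaires, given pre-BMT and then at four later visits: "Days 0, 7, 30 and 365 Patient Completes: BSI-18, BFI, BPI". Section 2.0 describes their content: "The patients will complete self-report measures assessing symptoms of psychological distress, pain and fatigue". The demographic form is marked as a caregiver form. Entry under section 4.1 covers "Any patient undergoing autologous or allogeneic HSCT" at the centre, with no limit on diagnosis, disease status or comorbidity. Section 8.1 plans 50 autologous and 50 allogeneic dyads, so transplant type is known for every patient.

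**The concern.** Illness severity is a plausible common cause of the exposure and the outcomes in objective 1.3. The protocol supplies half of this itself: objective 1.2 studies patient distress, fatigue and pain as influences on caregiver distress and burden. The other half, that sicker patients stay in hospital longer and die sooner, is a modest assumption. The plan does not connect the two objectives by adjusting one for the other.

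A t-test of hospital days by high and low burden, or a regression of hospital days on burden alone, would comply with section 8.2. Either could show a clear association when burden has no effect. With the causal wording of section 8.2, it would be reported as harm to the patient from caregiver burden.

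Timing adds a second route to the same error. Burden measured at Day 30 or Day 365 can follow the hospital stay and be a result of it. Baseline covariates do not repair that ordering.

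**Working it through.** **The plan's own figure.** 50 + 50 = 100 dyads. Sections 8.1 and 8.2 give no alpha, power, effect size, standard deviation or event rate, so nothing further can be reproduced. What follows is an illustration. The sample size comes from section 8.1; the two-sided 5% level and all correlations are assumptions.

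**Step 1: unadjusted analysis.** Let severity correlate *a* with burden and *a* with the outcome, with no effect of burden. The spurious correlation is r = a × a. On the Fisher z scale the test statistic is centred at atanh(r) × √(n − 3), and √97 = 9.85. The rejection rate is the probability that it falls beyond ±1.96.

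| a | r = a² | atanh(r) × 9.85 | False-positive rate |
|---|---|---|---|
| 0.2 | 0.04 | 0.39 | 6.8% |
| 0.3 | 0.09 | 0.89 | 14.4% |
| 0.4 | 0.16 | 1.59 | 35.6% |
| 0.5 | 0.25 | 2.52 | 71.1% |

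With only 50 complete dyads the rates are 5.9%, 9.5%, 19.8% and 41.7%. The spurious correlation is unchanged; there is only less power to detect it.

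**Step 2: transplant type alone.** Suppose the two equal groups differ by d₁ = 1 SD in hospital days and d₂ = 0.5 SD in burden, with no link within either group. Pooling gives r = 0.25·d₁·d₂ / √[(1 + 0.25·d₁²)(1 + 0.25·d₂²)] = 0.125 / √(1.25 × 1.0625) = 0.108, and a false-positive rate of about 19% at n = 100. Entering transplant type in the model removes this part.

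**Step 3: adjusting for a proxy.** Let a covariate correlate *p* with true severity and carry no other information. The remaining partial correlation is (a² − a²p²) / (1 − a²p²), tested with √(n − 4). For a = 0.5 and p = 0.5 this is (0.25 − 0.0625) / (1 − 0.0625) = 0.20.

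| a | No adjustment | Proxy, p = 0.5 | Good measure, p = 0.9 |
|---|---|---|---|
| 0.2 | 6.8% | 6.0% | 5.1% |
| 0.3 | 14.4% | 10.4% | 5.4% |
| 0.4 | 35.6% | 23.4% | 6.4% |
| 0.5 | 71.1% | 51.1% | 9.0% |

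A moderate proxy helps but leaves much of the excess. A good severity measure removes nearly all of it. The symptom scores and transplant type are therefore worth using, and clinical variables are worth adding.

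**Limits.** The model is a simple correlation on complete pairs. It speaks to length of hospitalization and only by analogy to survival.

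**The case against.** The strongest reply has four parts.

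- *The study does hold information related to severity.* Patients report distress, fatigue and pain at five time points, and transplant type is fixed by the accrual plan. This stands. A reader might infer that the study has no severity information at all, and the documents do not support that. They support only that no clinical severity variable is listed and that no use of the proxies is stated.
- *Silence does not show that clinical data will not be collected.* The section 5.0 table is a questionnaire schedule. Survival and length of hospitalization are missing from it too, although they are outcomes of objective 1.3, so it cannot be the full data list. The content of the demographic form is not shown. This also stands: the supportable statement is that these variables are not listed, and one cannot say that they will not be gathered. The serious-event reports in section 6 do not fill the gap, because section 6.0 ties its criteria to events caused by study participation.
- *Multiple regression is planned.* True, but regression controls only for what is entered, and an unadjusted comparison would also satisfy section 8.2.
- *Objective 1.3 is secondary, section 8.1 calls the work an initial analysis, and section 8.2 names no covariates for any objective.* This limits how serious the point is. It does not justify causal wording, and objective 1.3 is where the omission most directly changes the meaning of the result.

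**Conclusion.** The point holds as a gap in the analysis plan for a secondary objective. The plan poses a causal question in an unrestricted case mix, names no adjustment set, does not fix when the exposure is measured, and lists no clinical severity variable. An unadjusted analysis may be confounded by severity.

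A reader might go further and infer that the result will be confounded, or that the error is large. The documents give no correlation between severity and either burden or outcome, so neither follows. Under the assumptions above, the false-positive rate at 100 dyads runs from about 7%, close to nominal, to 71%.

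The change is worth making because the main covariates are already held and the rest need only a short abstraction. It does not affect the primary objective.

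**What to change.** In section 8.2:

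1. State that the exposure for objective 1.3 is caregiver burden and distress measured before the outcome period, with the pre-BMT assessment as the main exposure.
2. State that the length-of-hospitalization model adjusts for transplant type and the patient's pre-BMT BSI-18, BFI and BPI scores. Later patient scores may lie on the path from burden to outcome and should not be used for this.
3. State that the survival model adjusts for transplant type first and adds further covariates only as the number of deaths allows.
4. When hospital dates and deaths are taken from the centre's records, also abstract patient age, disease status at transplant and comorbidity. Use them as further covariates on the same basis, and list the abstraction with the section 5.0 schedule.
5. Replace the causal verb, here and in section 2.0, with 'is associated with, after adjustment'. Note that residual confounding remains because the proxies are imperfect.

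The cost is a few degrees of freedom, slightly wider intervals and a short chart abstraction for 100 patients at one centre. Item 4 changes the protocol's data collection as well as its analysis text.
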